6.7 Blinding

Blinding of the participants, care providers or the research team is not possible because the intervention requires identification of participants to receive text messages.

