NACOSTI:	National Council for Science Technology and Innovation
RCT:	Randomized controlled trial
TC:	Total cholesterol
TG:	Triglycerides
WHO:	World Health Organization

Abstract

Background

Approximately 552,400 (2.2%) adults aged between 20-79 years in Kenya have type 2 diabetes, 36.0% of the adults have undiagnosed diabetes. Diabetes considerably increases the risk to all-cause mortality and accompanying treatment leads to heavy economic costs. The use of mHealth in managing type 2 diabetes has been associated with increased adherence to diabetes medication, reduction in morbidity and increased self-monitoring of blood glucose in patients with type 2 diabetes.

Objectives

The objective of this study is to evaluate the efficacy of a diet-related mHealth intervention on glycated hemoglobin in adults with type 2 diabetes.

Methods

The mHealth intervention will be delivered using one-way and two-way mobile text messages that were systematically developed using the behavior change wheel to facilitate food literacy. The text messages are loss- or gain-framed to increase influences behavioral decisions. The primary outcome of this proof-of-concept randomized controlled trial will be glycated hemoglobin. Secondary outcomes include: i) anthropometric measurements (BMI, waist-hip ratio, and bioelectric Impedence analysis); ii) dietary intake of fruits, vegetables and legumes; iii) food literacy scores and iv) mHealth user satisfaction. Assessments shall be conducted at baseline, 3 months (primary endpoint) and 6 months (follow-up). To identify between-group differences, the generalized linear models will be determined using analysis of covariance through the intention-to-treat principle.

Study duration

This will be a 12-week intervention, that will be followed by a follow-up of the study cohort for another 12 weeks.

Budget

It is estimated that this study will cost approximately Kes 2,483,540.

1 Introduction/Background

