6.8.2 Control group

The control group will continue receiving standard care in the hospitals. The control group shall receive a reminder text messages one day before the routine clinic appointment. The clinic appointment dates shall be derived from the hospital where the participant receives routine diabetes care.

Figure 3 describes the study timeline and workflow. At the beginning of the intervention, both the control and intervention groups will receive introductory text messages. Text messages shall consist of personalized salutation (using the preferred name of the participant) sent to the officially registered mobile numbers. The messages shall be sent between 10am and 3pm through the Africa’s Talking® Application Programming Interface (API).

[figure not shown]

Figure 3. Study timeline

Table 2. Text messages for specific target behaviors

COM-B Components	What needs to happen for the target behavior to occur?	Behavior Change Technique	Text No	Text Messages	
Physical capability	Be able to select healthy food	Instructions on how to perform behavior	S 1	To meet nutrient needs within calorie limits, choose a variety of nutrient-dense foods across and within all food groups in recommended amounts. Energy dense foods include vegetables, fruits, whole grains, beans, nuts and seeds, and lean protein — when prepared with little or no saturated fats, added sugars and sodium	
			S 2	There are 5 food groups: (1)Vegetables and legumes or beans (2)Fruit; (3)Lean meats and poultry, fish, eggs, nuts and seeds, legumes or beans;(4) Grain (cereal) foods, mostly wholegrain or high cereal fiber varieties (5) Milk, yoghurt, cheese or alternatives, mostly reduced fat.	
			S 3	Reduce foods and beverages that are high in added sugars to better control your blood sugar. To avoid added sugars, check for words like brown sugar, corn sweetener, corn syrup, dextrose, fructose, and high-fructose corn syrup. These are added sugars	
			S 4	Reduce or avoid foods and beverages that are high in saturated fat like whole milk, cream, butter, cheese, meat, palm oil and coconut oil. Instead, select low-fat milk and use healthier plant-based oils.	
			S 5	Instead of selecting canned fruit or bottled juices, buy fresh juice or fruits as they are energy dense and have fiber that helps in blood sugar control. Fresh fruits are also cheaper.	

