6.9.2 Secondary Outcome measures

Secondary outcome measures will include biochemical, anthropometric and behaviour change measurements shall be measured at baseline and endline (end of week 12). Additionally, user-satisfaction shall be assessed at 12 weeks and 24 weeks post-intervention.

Biochemical measurements will include fasting plasma Glucose (FPG), total cholesterol (TC), triglycerides (TG), and high-density lipoprotein-cholesterol (HDL-C). FPG will be analysed by the glucose oxidase method using a Hitachi 7600, while TC, TG, HDL-C will be measured using the automatic blood analyser (Hitachi 736-40). Lab testing and analysis will be conducted at the Lancet laboratories, Kenya using standard procedures.

Anthropometric measurements will include weight, height, waist and hip circumferences that shall be measured by trained research assistants, and shall follow the CDC Anthropometry Procedures Manual (104). Additionally, bioelectrical impedance analysis shall be taken to determine body fat using the

Behaviour change shall be measured by changes in dietary intake of legumes, fruits and vegetables and through the mHealth Satisfaction Questionnaire (Appendix 6). The mHealth Satisfaction Questionnaire will be adopted from the questionnaire for assessing user satisfaction with mobile health apps (105).

7 Data Collection

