7.1 Quantitative Instruments

Various tools will be used to collect data. The socio-demographic and health questionnaire (Appendix 3), the food frequency questionnaire (Appendix 4) and the self-perceived food literacy questionnaire (Appendix 5) will be administered on all participants after enrolment. The socio-demographic and health questionnaire and the food frequency questionnaires have been piloted and used in studies in Kenya, while the self-perceived food literacy questionnaire shall be piloted during the study. These tools will be administered by trained research personnel in either Swahili or English, depending on the preference of the participant.

7.1.1 *Socio-demographic and health history questionnaire*

This study will utilize the electronic socio-demographic and health history questionnaire (Appendix 4) that was previously used in a sister study conducted in Makueni County, Kenya (Protocol number AMREF P424 2018). The questionnaire was developed based on the World Health Organization STEPS Instrument and Support Materials (106) and piloted in Makueni County, Kenya.

7.1.2 *Self-perceived food literacy questionnaire*

The self-perceived food literacy questionnaire is based on the tool used to assess the food literacy among people with chronic diseases in Netherlands (107). This tool was developed through an expert-based and theory-driven process and shall be piloted and adjusted before being used in the Kenyan settings. The responses options are a 5-point Likert scale where 1= 'not at all/never' to 5='yes/always' (Appendix 4).

7.1.3 *Anthropometric measurements*

Anthropometric measurements will be taken during the filling of the socio-demographic and Health history questionnaire. These measurements will include height, weight waist and hip circumference. Height and weight shall be used to calculate the body mass index (BMI).

7.1.4 *Body composition*

Body composition of all participants shall be taken at baseline and at the end of the intervention. The measurements shall be conducted by trained research assistants using the *Bodystat 500*[®] Body Composition Monitor.

7.1.5 *Blood samples*

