Two trained phlebotomists, each serving one hospital, will draw 5 ml venous blood using the closed vacuum extraction tubes with single-use needle and needle holder and following the WHO and Kenya Medical and Research Institute (KEMRI) guidelines(108). Laboratory requisition forms indicating the participant identification code shall be written for all the collected samples. The samples will be immediately stored in insulated coolers containing ice/cold packs at around 4°C. At the end of sample collection, the phlebotomists will centrifuge the blood samples and serum transferred into sterile cryo-vials in the two level 4 hospital laboratories. Two centrifuges shall be provided by the study, assigned to the two study phlebotomists. Thereafter the samples will be frozen at -20 degrees centigrade in study nitrogen tanks and transported to Lancet Laboratories[®] in Nairobi for analysis.

Phlebotomists will ensure hand hygiene by using pair of well-fitting clean disposable latex-free gloves, alcohol rubs, water and soap before after each blood draw to reduce risks of cross-contamination. Sufficient single-use disposable needles and sampling tubes will also be ensured for each blood sampling.

The study shall provide all required laboratory disposal equipment and materials.

Disposal of all lab waste will adhere to Laboratory Biosafety and Bisecurity Policy Guidelines (109). In brief the following measures shall be ensured in disposal of infectious wastes:

- i. Red infectious/biohazard waste disposal containers shall be located in each area of the laboratory where infectious waste may accumulate.
- ii. Containers shall be lined with disposable bright orange/red biohazard bags before placing infectious waste into them to prevent leakage.
- iii. Infectious waste containers shall not be filled more than three-quarters full.
- iv. Biohazard bags shall be removed from the work area after each day's use.
- v. Bags and containers shall be transport to the biohazard holding room as per the facility procedures.

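### Section 6.7 rules out blinding the whole research team for a reason that does not reach the staff who give the questionnaires or take tape measurements

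*Protocol*

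**What the plan says.** Section 6.7 is the only visible text on blinding: "Blinding of the participants, care providers or the research team is not possible because the intervention requires identification of participants to receive text messages".

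The passages that bear on it are these:

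- **Delivery (6.8.2).** "The messages shall be sent between 10am and 3pm through" a programming interface, to registered mobile numbers.
- **Questionnaires (7.1).** "These tools will be administered by trained research personnel in either Swahili or English". Section 7.2 trains research assistants and enumerators together over three days and describes the tools as interviewer-administered.
- **Anthropometry (6.9.2).** Weight, height, "waist and hip circumferences that shall be measured by trained research assistants".
- **Body composition (7.1.4).** Trained research assistants take it with a bioimpedance device.
- **Blood samples (7.1.5).** "Laboratory requisition forms indicating the participant identification code shall be written for all the collected samples".
- **Satisfaction (6.9.2).** "user-satisfaction shall be assessed at 12 weeks and 24 weeks post-intervention".
- **Objectives and outcomes.** A rise in the food literacy score is the second of two specific objectives (3.5). The Abstract lists food literacy, dietary intake and waist-hip ratio as secondary outcomes.

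**The concern.** The conclusion in 6.7 is wider than its reason. Someone must know who receives the texts. It does not follow that an interviewer or a person holding a tape measure must know. The protocol nevertheless declares the whole team unblindable, and no visible passage keeps assessors unaware of allocation.

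The outcomes at stake depend partly on the assessor. Many food literacy items in the appendix are confidence or frequency ratings, where prompting and tone can matter. Tape readings depend on placement and tension. If assessors know the arm and expect the texts to work, the arms can differ without any effect of the intervention. Analysis cannot repair this afterwards, so it has to be settled before data collection. The trial is also meant to supply parameters for a fully powered trial (6.3), and an unsupported statement that blinding is impossible could carry over into that design.

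**Working it through.** **1. Does the stated reason apply to each group?**

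| Group | Must know the arm for texts to be delivered? |
|---|---|
| Participants | Yes, they receive them |
| Staff who run messaging, make calls or handle replies | Yes |
| Staff who only administer questionnaires | No; the texts go through a software interface |
| Staff who only take tape measurements | No |
| Laboratory | No; samples carry a code |

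The reason therefore fails for the third and fourth rows, and these are where assessor discretion lies.

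**2. Which outcomes are exposed?** Food literacy, dietary intake, and waist and hip circumference. HbA1c, fasting glucose and lipids are assays. Weight, height and bioimpedance leave little discretion. The data form averages two tape readings, which reduces random error but not a shift linked to the arm. In the waist-hip ratio, errors in the same direction partly cancel.

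**3. How large could the effect be?** The protocol gives no figure for assessor bias, so there is nothing of its own to reproduce. Every shift and correlation below is an assumption. The arm size of 30 is from 6.3.

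*Unadjusted t-test.* In SD units, SE = √(2/30) = 0.258. With 58 df the critical t is 2.002, so the smallest significant difference is 2.002 × 0.258 = 0.517 SD. With no true effect and an assessor shift b at follow-up, the two-sided rejection rate comes from the noncentral t with noncentrality b/0.258.

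*ANCOVA on baseline* (equal variances at both visits, correlation ρ, 57 df). SE = √((2/30)(1 − ρ²)), which is 0.224 at ρ = 0.5 and 0.184 at ρ = 0.7. If the shift arises only at follow-up, the adjusted difference is biased by b. If the same shift is already present at baseline, the bias is b − ρb = b(1 − ρ).

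| Assumed shift b | 0.1 SD | 0.2 SD | 0.3 SD |
|---|---|---|---|
| t-test, shift at follow-up | 6.7% | 11.9% | 20.8% |
| ANCOVA ρ = 0.5, follow-up only | 7.2% | 14.2% | 26.1% |
| ANCOVA ρ = 0.7, follow-up only | 8.3% | 18.7% | 35.9% |
| ANCOVA ρ = 0.5, both visits | 5.6% | 7.2% | 10.1% |
| ANCOVA ρ = 0.7, both visits | 5.3% | 6.2% | 7.7% |

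The nominal rate is 5% throughout. Table 4 lists recruitment and allocation above baseline data collection, so assessors may know the arm at baseline too. The timing cells are not legible, so this is a possibility and not a fact.

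**4. How much could masking recover?** For self-reported outcomes it removes only the assessor's share. If the total bias were 0.3 SD and that share 25%, 50% or 75%, the remaining shift is 0.225, 0.15 or 0.075 SD, and the t-test rate falls from 20.8% to 13.7%, 8.8% or 5.9%.

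**5. Is it feasible?** The budget in 10.4 lists four enumerators for 14 days: 4 × 14 = 56 person-days. Sixty participants make 120 visits over two rounds (6.9.2) or 180 over three (Abstract), which is 120/56 = 2.1 to 180/56 = 3.2 visits per person-day. If the three training days come out of the 14, there are 4 × 11 = 44 person-days and 2.7 to 4.1 visits per person-day. Both figures assume that the 14 days cover all rounds.

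**The case against.** The strongest reply is that little is at stake. The primary outcome is a coded laboratory assay. Section 6.3 says that hypothesis testing was not the aim, and 8.2 specifies ANCOVA only for HbA1c; only the Abstract mentions ANCOVA in general terms. A false-positive rate for food literacy is therefore a loose yardstick. The food literacy scale is self-perceived, has fixed response options and is answered by people who know their arm, so the respondent's own bias probably dominates. Participants who have received 36 dietary texts may well reveal their arm while answering diet questions.

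Much of this stands. It limits the weight of the point and shows that masking would be partial. It does not supply the missing reason: 6.7 still calls blinding impossible for staff to whom its argument does not apply.

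Two stronger readings are tempting. A reader might infer that the same people send the texts and assess the outcomes. The visible text does not say so, and the team-roles section (10.1) is not in the text at hand. A reader might also take the t-test rates as a lower bound because ANCOVA is more precise. That holds only if the shift is confined to follow-up; with the same shift at baseline, the ANCOVA rates fall below the t-test rates.

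**Conclusion.** The point holds as a low-cost improvement to the design. The reason in 6.7 supports leaving participants and messaging staff unmasked, and by extension care providers can reasonably stay on that list. It does not support leaving questionnaire and tape-measure assessors unmasked. Following the plan as written leaves avoidable assessor bias in specific objective 2 and in the dietary and waist-hip outcomes.

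The size is not known. Under the assumed shifts of 0.1 to 0.3 SD, the false-positive rate ranges from barely above 5% to 35.9%, depending mainly on the size of the shift and on whether it is also present at baseline. The conclusion rests on the text and not on these numbers. It would be wrong to infer that the HbA1c comparison is compromised, or that masking assessors would remove the bias: respondent bias from unmasked participants would remain.

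**What to change.** Restate 6.7 along these lines:

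> Participants, care providers and staff who handle messages, calls or replies cannot be masked. Staff who administer the food literacy and dietary questionnaires or take tape measurements are kept unaware of allocation and have no access to the allocation list or the messaging system.

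If the investigators believe that this cannot be done, 6.7 should give a reason that applies to those staff.

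Where the research assistant handles messaging, the budgeted and trained enumerators can do these assessments. Section 6.9.2, which assigns the tape measurements to research assistants, would then need matching wording. The satisfaction questionnaire asks about the intervention and can reveal the arm, so it should come after the other assessments at a visit and, where staffing allows, be given by someone else.

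The change needs no extra staff that the budget shows to be lacking, and no change to sample size or intervention. It costs some rota flexibility. Its benefit is partial, since participants may disclose their arm. Whether the separation fits the actual division of work should be checked against the team-roles section.

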6.8 Interventions

6.8.1 Intervention group

The intervention group will receive a total of 43 text messages as tabulated in Table 1 below. Text messages were developed using the BCW through a systematic process linked to specific behavior change techniques (Table 2). The text messages will provide practical information or guidance to influence selection and eating healthy diet for type 2 diabetes care. The text messages were either loss- or gain-framed to increase influence on behavioral decisions (103). Additionally, the participants will receive a text message to rate their ability on selection of food and eating of healthy diet based on the messages received in the month. The combination of the one-way and two-way messages in this group are designed to increase engagement of the participants.

Table 1. Text Messages Schedule

Message type	Message format	Frequency	Total number of messages
Introductory message	One-way	Once	1
Clinic Appointment	One-way	1 message per month	3
Selection of healthy food	One-way	3 messages per week	18
Eating healthy diet	One-way	3 messages per week	18
Evaluation message	Interactive	1 message per month	3

6.8.2 Control group

The control group will continue receiving standard care in the hospitals. The control group shall receive a reminder text messages one day before the routine clinic appointment. The clinic appointment dates shall be derived from the hospital where the participant receives routine diabetes care.

Figure 3 describes the study timeline and workflow. At the beginning of the intervention, both the control and intervention groups will receive introductory text messages. Text messages shall consist of personalized salutation (using the preferred name of the participant) sent to the officially registered mobile numbers. The messages shall be sent between 10am and 3pm through the Africa’s Talking® Application Programming Interface (API).

[figure not shown]

Figure 3. Study timeline

Table 2. Text messages for specific target behaviors

COM-B Components	What needs to happen for the target behavior to occur?	Behavior Change Technique	Text No	Text Messages	
Physical capability	Be able to select healthy food	Instructions on how to perform behavior	S 1	To meet nutrient needs within calorie limits, choose a variety of nutrient-dense foods across and within all food groups in recommended amounts. Energy dense foods include vegetables, fruits, whole grains, beans, nuts and seeds, and lean protein — when prepared with little or no saturated fats, added sugars and sodium	
			S 2	There are 5 food groups: (1)Vegetables and legumes or beans (2)Fruit; (3)Lean meats and poultry, fish, eggs, nuts and seeds, legumes or beans;(4) Grain (cereal) foods, mostly wholegrain or high cereal fiber varieties (5) Milk, yoghurt, cheese or alternatives, mostly reduced fat.	
			S 3	Reduce foods and beverages that are high in added sugars to better control your blood sugar. To avoid added sugars, check for words like brown sugar, corn sweetener, corn syrup, dextrose, fructose, and high-fructose corn syrup. These are added sugars	
			S 4	Reduce or avoid foods and beverages that are high in saturated fat like whole milk, cream, butter, cheese, meat, palm oil and coconut oil. Instead, select low-fat milk and use healthier plant-based oils.	
			S 5	Instead of selecting canned fruit or bottled juices, buy fresh juice or fruits as they are energy dense and have fiber that helps in blood sugar control. Fresh fruits are also cheaper.	
	Be able to eat healthy food diet			E1	To ensure you eat a healthy diet, try to eat the following food servings most days of the week: (1) Vegetables and legume beans: Like 5-6 medium cups of managu, or mixed vegetables, or 2 tomatoes. (2) Fruits: Like 2 medium size apples, bananas, oranges or pear. (3)Lean meats and poultry, fish, eggs, nuts and seeds, legumes or beans: Like 200g raw meat or fish, or 2 eggs, or 60g of nuts or 300g beans ; (4) Whole meal grain (cereal) foods: Like 60–90 g of Ugali, bread, chapati (5) Milk, yoghurt, cheese or alternatives: like 500 ml milk or yoghurt
				E 2	Most processed carbohydrate foods release glucose more quickly than whole grain carbohydrates. Eat whole grain carbohydrates which produce a slower rise in blood glucose levels, which are called low-glycemic index (GI) foods and result in better blood glucose control.
				E 3	Low GI foods include some posho milled unga, high-fiber breads and whole meal cereals githeri, most fruits, legumes, and low-fat dairy products
				E 4	Eating vegetables before a carbohydrate rich meal has been shown to have beneficial effects on blood sugar levels. This practice slows down the speed at which carbs are absorbed into the bloodstream and may benefit both short- and long-term blood sugar control.

			E 5	Eat fruits instead of making fruit juice. Fruits contain fiber and various plant compounds. Sugar from fruits is generally digested very slowly and do not cause increases in blood sugar levels.		
			E 4	Limit pork, lamb, beef meats: instead, eat plant-based proteins like beans, green peas, green grams or animal proteins like eggs or fish. Pork, lamb, beef meats contain saturated fats		
			E 6	Limit lard/bacon /chicken fat/butter, instead, vary with liquid vegetable-based oils: Use olive oil or vegetable oil for cooking. Limit lard, bacon, chicken fat and butter contain saturated fats		
			E 7	Eat regular meals and spread out your servings of energy giving foods evenly throughout the day. This helps you can maintain energy levels without causing large rises in blood glucose levels.		
Psychological capability	Know healthy food	Information about health consequences	S 6	The amount of carbohydrate in your meal has the greatest effect on blood glucose levels. Avoid big servings of carbohydrates in your meal and ensure most of your energy giving foods are composed of whole meal or high fiber. Make vegetables and fruits take the larger portion of your plate.		
			S 7	There are two main types of fat: saturated and unsaturated. Too much saturated fat in foods like fatty meat, sausages and butter can increase the amount of cholesterol in the blood, which increases your risk of developing heart disease.		
			S 8	Instead of selecting foods with saturated fats, select foods with unsaturated fats like nuts, seeds, seafood, and avocados.		
			Advanced planning skills to ensure selection of food healthy food		S 9	Some food items like sauces have hidden sugar and salt, therefore it is wise to avoid tomato sauces, fat-free salad dressings, and condiments. Instead of sauces. To improve the taste of your food, select preferred spices, herbs, onions, or other low-energy flavorings
				S 10	Select whole or minimally processed foods, which help to control your blood glucose	
				S 9	Make an eating plan each week – this is the key to fast and easy meal preparation. This will also ensure that you plan for healthy diets and better controlled blood glucose.	
				S 11	Plan to have meals with plenty of vegetables and fruit. Your goal is to fill half your plate with vegetables and fruit at every meal. Choose colored fruits like oranges, mangoes, loquats, plums and vegetables like managu, carrots and tomatoes.	
	Know the composition of the plate model		E 8	Start with a 9-inch dinner plate Fill half with non-starchy vegetables, such as managu, Sukuma wiki , green beans, broccoli, cauliflower, cabbage, and carrots. Fill one quarter with a lean protein, such as chicken, fish, legumes or beans, or eggs. Fill one quarter with whole meal carbohydrate foods: grains, starchy vegetables (such as potatoes and peas), rice, pasta, beans, fruit, and yogurt. A cup of milk also counts as a carb food.		
Social Opportunity	Change cultural habits on portion size	-Goal setting (behavioral) -Restructuring the physical environment	S 12	Controlled portion sizes of food are important to reducing calorific intake. To control your portion sizes, plan to use a smaller plate size when serving meals.		
			S 13	Your health is a personal responsibility. When eating, try to avoid places that may entice you to eat excessive food. Eat most of your meals at home for better control of healthy food and your blood sugar		

Reflective motivation	Intend to select healthy diet	-Information about health consequences -prompts/cues	S 14	Make your shopping list ahead of time and do not go shopping while hungry. This helps you to buy healthier items but also save money and select healthier foods.
			S 15	Intend to purchase less saturated and unhealthy fats by using oils like canola, corn, olive, peanut, safflower, soybean, and sunflower oils. Unsaturated oils that are healthy and are also naturally present in nuts, seeds, seafood, and avocados.
			S 16	Intend to select healthy dietary pattern by selecting foods and beverages that have low or no added sugars, saturated fat, and/or sodium. Check food labels to check the nutrient content of the food items.
			S 17	Instead of purchasing processed grade 1 flour or unga, use posho mill unga. It contains fiber and other plant extracts that are important to the body and blood sugar control.
	Intend to prioritize eating healthy diet		E 9	Small changes to more nutrient-dense, single food and beverage choices combine to become a nutrient dense meal, and can lead to a whole day made up of nutrient-dense meals and snacks, increasing you blood sugar control
			E 10	Place fresh and locally available low-carbohydrates fruits on the table or where they are easy to reach to increase intake of fruits. This enables you to eat healthy and avoid unhealthy snacking.
			E 11	To reduce salt intake, ensure that salt is added to food when cooking. Avoid having saltshakers on the table when eating
			E 12	A supportive family enables you to eat healthy meals. Enlist your family members to support you to encourage your intake of healthy meals by planning meals and eating together.
			E 13	Portion sizes of food affect the calories consumed. Plan to control your portion sizes by using smaller plates and ensuring that you apply the plate model in serving your various foods
			E 14	Water is important to prevent dehydration and aid in the digestion of food and absorption of nutrients. To increase water intake, flavor your water with fruits like lemon or orange.
Automatic motivation	Establish routines and habits to select healthy diet	Instructions on how to perform behavior	S 18	Keep a food diary for a few days to evaluate what you eat every day. Note how you were feeling when you ate – hungry, not hungry, tired, or stressed? Create a list of “cues” by reviewing your food diary to become more aware when you’re “triggered” to eat for reasons other than hunger. Is there anything else you can do to avoid the cue or situation? If you cannot avoid it, do something differently that would be healthier. Replace unhealthy habits with new, healthy ones
			Restructuring the physical environment Prompts/Cues	S 18
			E 15	Eat smaller meals more often. Eat at least three meals a day with snacks in between. When you wait too long to eat you are more likely to make unhealthy food choices.

	Establish routines and habits to serve and eat healthy diet		E 16	Make a routine of eating healthy snacks like groundnut or almonds, yogurt, or yogurt with berries, hard-boiled eggs, avocado, or fruit slices. These snacks help you to maintain your blood sugar and reduce extra energy intakes.
			E 17	Eating at home, or carrying safe food when traveling ensures that you eat healthy diets that make you control your blood sugar
			E 18	Alcohol consumption can worsen diabetes-related medical complications, such as disturbances in fat metabolism, nerve damage, and eye disease. Avoid or limit alcohol to have optimal blood sugar control
Two-way messages			Month 1	Looking at the messages you have received this month, rate your confidence in selecting of healthy diets 1 2 3 4 5
			Month 2	Looking at the messages you have received this month, rate your ability to eat healthy dietary choices for diabetes care 1 2 3 4 5
			Month 3	Looking at the messages you have received this month, rate your general knowledge relating to selection and eating of health diet 1 2 3 4 5

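### Text E5 in Table 2 wrongly tells participants with type 2 diabetes that fruit sugar does not raise blood sugar, against four other texts in the same table

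*Protocol*

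**What the plan says.** Section 6.8.1 makes the text messages the treatment in the intervention arm. Table 2 then gives their wording, with S numbers for selecting food and E numbers for eating it.

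E5 advises whole fruit in place of home-made juice, mentions fiber and plant compounds, and closes with: "Sugar from fruits is generally digested very slowly and do not cause increases in blood sugar levels".

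Four other texts in Table 2 bear on the same matter:

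- **E2**, on grains: "Eat whole grain carbohydrates which produce a slower rise in blood glucose levels, which are called low-glycemic index (GI) foods".
- **E3**, on which foods qualify: "Low GI foods include some posho milled unga, high-fiber breads and whole meal cereals githeri, most fruits, legumes, and low-fat dairy products".
- **S6**, on what drives glucose: "The amount of carbohydrate in your meal has the greatest effect on blood glucose levels".
- **E8**, the plate model, lists the foods for its carbohydrate quarter: grains, then "starchy vegetables (such as potatoes and peas), rice, pasta, beans, fruit, and yogurt".

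Section 4 states the mechanism: the texts are expected to change how participants select and eat food, and so lower HbA1c. Section 6.9.1 makes HbA1c the primary outcome.

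**The concern.** In most protocols a loose sentence about nutrition would be background. Here the sentence is part of the treatment, sent to the phones of people diagnosed with type 2 diabetes within the previous year (section 6.2.2). Read literally, E5 says that fruit has no effect on blood sugar, so that its amount does not matter for glycemic control.

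Readers may be poorly placed to notice the error. Section 3.3 cites a Kenyan study of people with type 2 diabetes in which 69.3% had low nutrition knowledge and 81.4% did not know what a balanced diet is. Section 7.3 also commits the investigators to procedures that do not expose participants to needless risk. At stake are the accuracy of the advice given to patients and the internal consistency of the intervention.

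**Working it through.** The Protocol gives no figure to reproduce here and no power or sample-size formula applies. The check compares the texts.

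**Step 1: what E5 asserts.** The last sentence has two clauses. The word meaning *in general* attaches to the speed of digestion. The second clause, on blood sugar, has no qualifier and no comparison with juice. As written, it denies any rise.

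**Step 2: comparison with the other texts.**

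| Text | What it implies about fruit | Compatible with no rise? |
|---|---|---|
| E8 | Fruit is a carbohydrate food and belongs in the carbohydrate quarter | Not when read with S6 |
| S6 | Carbohydrate amount is the strongest influence on blood glucose | Not when read with E8 |
| E2 | Low-index foods give a slower rise | No: slower is not absent |
| E3 | Most fruits, not all, are low-index | No: the rest lack even that property |

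E8 and S6 together suffice. If fruit is a carbohydrate food, and carbohydrate amount is the main driver of blood glucose, fruit cannot be without effect. E2 and E3 lead to the same result separately. E2 is written about whole grains, but E3 places most fruits in the same low-index class, and the property given for that class is a slower rise.

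E10 points the same way by steering readers to fruits low in carbohydrate. That advice would have no purpose if E5 were right.

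**Step 3: extent.** One text (E5) contains the wrong statement. The planned intervention arm is 30 participants (section 6.3), so at most 30 would receive it. Receipt by all is not certain, because section 7.1.6 lets the monthly reply determine the type of message sent next.

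No percentage of texts is given. Table 1 counts 18 + 18 = 36 content texts. Table 2 repeats the labels E4, S9 and S18, and the two E4 entries and two S9 entries carry different wording, so it prints at least 36 + 2 = 38. There is no single firm denominator.

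**Step 4: does the placement of fruit on the plate also conflict?** E8 gives half the plate to vegetables ("Fill half with non-starchy vegetables, such as managu"), one quarter to protein and one quarter to carbohydrate foods including fruit: 1/2 + 1/4 + 1/4 = 1.

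- S6 says: "Make vegetables and fruits take the larger portion of your plate". On an E8 plate, vegetables and fruit together take at least 1/2, and more once any fruit is added in the carbohydrate quarter. E8 is therefore one way to follow S6.
- S11 says: "Your goal is to fill half your plate with vegetables and fruit at every meal". An E8 plate meets this too. The reverse need not hold, because S11 lets fruit use part of the half that E8 keeps for non-starchy vegetables. S11 gives no split. If the E8 carbohydrate quarter is kept as well, carbohydrate foods including fruit could take from 1/4 to just under 1/4 + 1/2 = 3/4 of the plate. The upper end assumes a half filled almost wholly with fruit, which S11 does not suggest, since it also asks for plenty of vegetables.

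S11 is looser than E8, not opposed to it.

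**The case against.** The strongest defence is context. What E5 asks people to do, eat fruit and not juice it, is sound and fits its fiber rationale. The faulty clause is a closing explanation, and the authors probably meant that whole fruit raises glucose more slowly than juice. E5 also sits among correct advice: E1 suggests about two medium pieces of fruit on most days, S6 warns against large carbohydrate servings, and E8 says plainly that fruit is a carbohydrate food.

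This limits the likely practical effect, but it does not correct the sentence. Participants receive separate messages over weeks and do not see the table as a whole. The intended comparison with juice is not in the sentence.

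A reader might infer three stronger points, which the document does not support:

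- **That the plate advice contradicts itself across S6, S11 and E8.** An E8 plate satisfies both S6 and S11. Nothing in the Protocol says that E8 must govern the other two. E13 tells participants to apply the plate model, which makes E8 a reasonable reference but no more than that.
- **That S5 contradicts E5 on juice.** S5 contrasts fresh produce with canned fruit and bottled juice, while E5 contrasts whole fruit with juice. S5 leaves in a poorer option, but it does not give the opposite instruction.
- **That the error biases the HbA1c result.** The Protocol offers no basis for estimating any such effect, in size or direction.

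**Conclusion.** The point holds for E5 alone. One sentence makes an unqualified and wrong statement about blood sugar to people with diabetes, and E2, E3, S6 and E8 show it to be wrong without any outside source. The only assumption is that those four texts say what the investigators mean, which is reasonable because they agree with one another.

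The fault is small in extent but lies in what the trial delivers, so it should be corrected before the texts go out. No effect on HbA1c is claimed. The difference between S11 and E8 merits an optional note only, and neither S5 nor S6 needs to change.

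**What to change.** Before the texts are sent, replace the last sentence of E5 with:

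*Sugar from whole fruit is generally digested slowly and raises blood sugar more slowly than juice, but fruit still counts as a carbohydrate food.*

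This keeps the advice to prefer whole fruit and brings E5 into line with E2, E3, S6 and E8. The cost is re-approval of one amended text, with no extra visits, staff or participants.

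Optionally, the investigators may align S11 with E8 on whether fruit shares the vegetable half of the plate. That is a dietary choice for them. Moving fruit to the carbohydrate quarter could dampen fruit intake, which section 6.9.2 measures as a secondary outcome.
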